6.14.5. Vital Signs and Other Physical Characteristics

Vital signs include systolic blood pressure, diastolic blood pressure, pulse, and temperature. Physical characteristics include weight and BMI.

Vital signs and physical characteristics will be summarized and analyzed for the following periods:

- Induction Period
- Maintenance Period
- Extension Period

Vital sign and physical characteristic results will be provided in a by-patient listing.

BMI will be calculated using the following formula.

$$\text{BMI (kg/m}^2\text{)} = \text{weight (kg) divided by the square of the height (m).}$$

Values at each visit (starting at randomization) and change from baseline to each visit for vital signs and physical characteristics will be displayed in box plots (notched box for each treatment with outliers displayed) for patients who have both a baseline and a result for the specified visit. Individual measurements outside of reference limits will also be displayed using distinct symbols overlaying the box plot. Baseline is defined as the last non-missing assessment recorded on or prior to the first study drug injection at Week 0 (Visit 2). Original-scale data will be used for the display. Unplanned measurements will be excluded. The following summary statistics will be included in a table below the box plot: N, mean, standard deviation, minimum, Q1, median, Q3, and maximum. Box plots will be used to evaluate trends over time and to assess a potential impact of outliers on central tendency summaries.

Change from baseline to last observation will also be summarized within the box plot of changes (rightmost column) for patients who have both baseline and at least one post-baseline result. Baseline is defined as the last non-missing assessment recorded on or prior to the first study drug injection at Week 0 (Visit 2). The last non-missing observation in the treatment period will be used as the last observation. Original-scale data will be used. Unplanned measurements will be excluded. A p-value will be included in the summary statistics at the bottom of the box plot for this assessment, using an ANCOVA model containing terms for treatment and the continuous covariate of baseline measurement. The percentages of patients with treatment-emergent high or low vital signs and physical characteristics results at any time will be summarized. A treatment-emergent high result is defined as a change from a value less than or equal to the high limit at all baseline visits to a value greater than the high limit at any time that meets the specified change criteria during the treatment period. A treatment-emergent low result is defined as a change from a value greater than or equal to the low limit at all baseline visits to a value less than the low limit at any time that meets the specified change criteria during the treatment period. To assess increases, change from the maximum value during the screening period to the maximum value

during the treatment period will be used. To assess decreases, change from the minimum value during the screening period to the minimum value during the treatment period will be used. Tables 5 will be used to define the low and high limits and change thresholds.

Additionally, values at each visit (starting at randomization) and change from baseline to each visit for vital signs and physical characteristics will be displayed in box plots (with outliers displayed) for patients who have both a baseline and a result for the specified visit. Baseline is defined as the last non-missing assessment recorded on or prior to the first study drug injection at Week 0 (Visit 2). Original-scale data will be used for the display. Unplanned measurements will be excluded. Reference limits will not be displayed. The following summary statistics will be included in a table below the box plot: N, mean, standard deviation, minimum, Q1, median, Q3, and maximum. Box plots will be used to evaluate trends over time and to assess a potential impact of outliers on central tendency summaries.

Table 5 Categorical Criteria for Abnormal Treatment-Emergent Blood Pressure and Pulse Measurement, and Categorical Criteria for Weight and Temperature Changes for Adults

Parameter	Low mmHg	High mmHg
Systolic BP (mm Hg) (Supine or sitting – forearm at heart level)	≤ 90 and decrease from baseline ≥ 20	≥ 140 and increase from baseline ≥ 20
Diastolic BP (mm Hg) (Supine or sitting – forearm at heart level)	≤ 50 and decrease from baseline ≥ 10	≥ 90 and increase from baseline ≥ 10
Pulse (bpm) (Supine or sitting)	< 50 and decrease from baseline ≥ 15	> 100 and increase from baseline ≥ 15
Weight (kg) (Consistent clothing and timing in relationship to meals and voiding)	(Loss) decrease $\geq 7\%$	(Gain) increase $\geq 7\%$
Temperature	< 96 degrees F and decrease ≥ 2 degrees F	≥ 101 degrees F and increase ≥ 2 degrees F

6.14.6. Electrocardiograms

Detailed Electrocardiogram results are part of the clinical database for this study. Should an ECG be performed in association with an AE or medical history event, the occurrence of the ECG (“Yes/No”) will be provided in a by-patient listing.

If any clinically significant ECG measurement occurs, this will be recorded as an AE. ECG data will not be analyzed.

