Safety: The following safety measures will be assessed in this study: AEs; SAEs; vital signs; electrocardiograms (ECGs); physical examinations; and laboratory safety evaluations including chemistry, hematology, and urinalysis.

Health Outcomes: The following health outcomes measures will be assessed in this study: Patient's Global Impressions of Severity score, Patient's Global Impressions of Improvement score, Inflammatory Bowel Disease Questionnaire score, and 36-Item Short Form Health Survey score.

Pharmacokinetic: Serum for the measurement of LY3074828 time-concentration profiles will be collected as specified in the visit schedule.

Statistical Methods:

Statistical: Approximately 240 subjects will be randomized to 1 of 4 double-blind treatment regimens: placebo, 50 mg LY3074828 exposure-based dosing, 200 mg LY3074828 exposure-based dosing, or the 600-mg LY3074828 fixed-dose treatment group in a 1:1:1:1 ratio (~60 subjects per arm). Approximately one-third are to be biologic-naive subjects (~20 per arm) and approximately two-thirds are to have been exposed to at least 1 previous biologic agent (~40 per arm).

Efficacy analyses will be conducted on the intent-to-treat population. Safety analyses will be conducted on the safety population. Subjects will be analyzed according to the treatment to which they were assigned.

All tests of treatment effects will be conducted at a 2-sided alpha level of 0.05 unless otherwise stated. Summary statistics for continuous variables may include mean, standard deviation, median, and minimum and maximum

values; categorical variables will be presented as counts and percentages.

Efficacy: The rates of remission and nonremission will be summarized by dose level and previous biologic use (yes/no). For categorical measures of efficacy, the differences between each treatment arm and placebo will be tested separately via a logistic regression model that controls for previous biologic use.

Safety: Safety will be assessed by evaluating all reported AEs and changes in laboratory analytes, ECGs, and vital signs (including body weight). Duration of exposure to therapy will be calculated for each subject and summarized by treatment group.

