10.3.2.4. Electrocardiograms

For each subject, 12-lead digital ECGs will be collected according to the study schedules ([Attachment 1](#) and [Attachment 2](#)). Subjects should be supine for approximately 5 to 10 minutes before ECG collection and remain supine but awake during ECG collection.

ECGs may be obtained at additional times when deemed clinically necessary. Collection of additional ECGs at a particular time point is allowed when needed to ensure high quality records.

ECGs will be interpreted by a qualified physician (the investigator or qualified designee) at the site as soon after the time of ECG collection as possible and ideally while the subject is still present, to determine whether the subject meets entry criteria and for immediate subject management should any clinically relevant findings be identified.

After enrollment, if a clinically significant increase in the QT interval or corrected QT interval or other clinically significant quantitative or qualitative change from baseline is present, the investigator will assess the subject for symptoms (eg, palpitations, near syncope, syncope) and to determine if the subject can continue in the study. The investigator or qualified designee is responsible for determining if any change in subject management is needed and must document his/her review of the ECG printed at the time of evaluation. Clinically significant increase in the QT interval or corrected QT interval should be recorded as an AE.

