12.2.8. Safety Analyses

Safety will be assessed by evaluating all reported AEs and changes in laboratory analytes, ECGs, and vital signs (including body weight).

Duration of exposure to therapy will be calculated for each subject and summarized by treatment group.

AEs will be coded according to the *Medical Dictionary for Regulatory Activities* and summarized by system organ class, preferred term, severity, and relationship to investigational product. A TEAE is defined as an event that first occurred or worsened in severity after baseline. In the analysis of TEAEs during the induction period, all preexisting conditions recorded at screening (Visit 1) and any on-study AEs recorded at or before baseline (Visit 2) will be used as baseline. In the analysis of TEAEs during the maintenance period, any on-study AEs recorded at Week 12 will be used as baseline. The induction period and the maintenance period will be analyzed separately. For each event classification term, the number of subjects experiencing a TEAE with that classification term will be tabulated. Treatment-related TEAEs are defined as events that are indicated by the investigator on the CRF to be related to treatment. If a subject reports the occurrence of a particular event more than once, the most severe of those events will be included in the summary tables of TEAEs, and the most severe of the most related of those events will be included in the summary tables of treatment-related events. TEAEs of interest will be presented.

Additional safety parameters include laboratory test results, ECGs, and vital-sign measurements. The baseline for computing the change in safety variables for the induction period will be data collected at or before dosing on Visit 2; the baseline for the maintenance period will be the last value collected during the induction period. The parameters will be listed and summarized with standard descriptive statistics. Change from baseline will also be summarized by randomized treatment.

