6.18. Changes to the Planned Analysis from the Clinical Study Protocol

The primary analysis method for categorical variables will now be logistic regression not CMH.

Prior Concomitant and Current Concomitant medication will not be summarized as reported in section 12.2.4 of the protocol. Prior Medication and Concomitant medications will be summarized per section 6.10 of the SAP.

As of the approval date of SAP version 3, there are no additional changes to the planned analysis in the protocol.

7. Unblinding Plan

A limited number of pre-identified individuals at Eli Lilly and Company may gain access to the unblinded data as part of the prespecified interim analysis (see section 6.17) in order to initiate the final population PK/PD model development processes for primary analyses and/or to evaluate safety data. Information that may unblind the study during the analyses will not be reported to study sites until the Maintenance period has been completed.

Additionally, a limited number of pre-identified individuals, an Eli Lilly and Company PK/PD Scientist and unblinded site pharmacists will have access to patients dosing information in order to conduct the TDM adjustments. Unblinded dosing information will not be shared with any other study or site personnel.

8. References

- [2] Frank-Bretz et al., Graphical approaches for multiple comparison procedures using weighted Bonferroni, Simes or parametric tests,, *Biometric Journal* 53 (2011) 6, 894-913. Al
- [2]. Mohamed Aloh et., Advanced multiplicity adjustment methods in Clinical trials,, *Statistics in Medicine*, Published on line 16 September 2013 in Wiley Online Library.
- [3]. Mosli M et al., Development and validation of a histological index for UC, *Gut* 2015, 0:1-9.
- [4]. Travis et al., Developing an instrument to assess the endoscopic severity of ulcerative colitis: the Ulcerative Colitis Endoscopic Index of Severity (UCEIS), *Gut* 2012, 535-42.

9. Appendices

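### SAP 6.14.6 drops the by-arm ECG summaries that Protocol 12.2.8 plans, and SAP 6.18 does not declare the change

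*SAP*

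**What the plan says.** **Protocol.** The synopsis counts ECGs among the safety measures: "The following safety measures will be assessed in this study: AEs; SAEs; vital signs; electrocardiograms (ECGs); physical examinations". Section 10.3.2.4 requires them of everyone: "For each subject, 12-lead digital ECGs will be collected according to the study schedules". Section 12.2.8 then says how they are to be handled. It first groups them with two other data types: "Additional safety parameters include laboratory test results, ECGs, and vital-sign measurements". It then sets one analysis for the group: "The parameters will be listed and summarized with standard descriptive statistics. Change from baseline will also be summarized by randomized treatment".

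**SAP.** Section 6.14.6 opens with "Detailed Electrocardiogram results are part of the clinical database for this study". It next provides a by-patient listing of whether an ECG was done when one accompanied an adverse event or a medical-history event, and it closes with "If any clinically significant ECG measurement occurs, this will be recorded as an AE. ECG data will not be analyzed". Section 6.14 lists the measures by which safety and tolerability will be evaluated, and ECG is not one of them. Section 6.18 records two departures from the protocol (logistic regression in place of CMH, and the concomitant-medication summaries). It then says that, at approval of version 3, "there are no additional changes to the planned analysis in the protocol".

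**The concern.** A safety summary that the protocol plans has been removed, and the section whose job is to record such removals says that nothing else changed. Someone writing the study report from SAP 6.18 would not know that there is a departure to explain.

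The practical loss is the view of average change. Under the SAP, an ECG effect reaches a by-treatment table only if a site physician judges an individual tracing clinically significant and records an adverse event. A moderate mean shift in an ECG interval on LY3074828 relative to placebo, spread over many patients and below anyone's threshold for an event, would not be displayed. The induction period is where such a shift could be set against a concurrent randomised placebo arm.

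**Working it through.** The documents give no ECG figure to reproduce. The check is a comparison of texts, followed by a count and one illustration.

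**1. What was collected.** From the schedules:
- Protocol Attachment 1, screening and induction: Visits 1, 2 and 7.
- Protocol Attachment 1, maintenance and follow-up: Weeks 32, 52, 80, 104 and 120.
- Protocol Attachment 2, extension: Extension Weeks 0, 11–12, 32, 40, 72, 92 and 108.

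**2. Planned against retained.** Protocol 12.2.8 treats three data types alike.

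| Data type | Protocol 12.2.8 | SAP |
|---|---|---|
| Laboratory tests | Descriptive summary and change from baseline by arm | Kept (6.14.4): values and changes by visit and treatment |
| Vital signs | Same | Kept (6.14.5): values and changes by visit and treatment |
| ECGs | Same | Dropped (6.14.6) |

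Only ECG loses its summary, and no reason is given.

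**3. Whether the change is declared.** Protocol 12.2.1 and SAP 6.1 let a change that does not affect a principal feature be made without a protocol amendment, provided that the study report describes and justifies it. SAP 6.18 records even the change to concomitant-medication summaries, but not this one. Its statement that nothing else changed is therefore incorrect.

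**4. Count of tracings without a by-arm summary.** With about 240 patients randomised, 240 × 3 = 720 tracings at Visits 1, 2 and 7, which gives up to 240 pairs of Visit 2 and Visit 7 values. Both are upper limits, because they assume that every patient attends Visit 7.

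**5. What a summary could show (illustration only).** The documents give no standard deviation for QTc change. Assume 15 to 20 ms and complete data, with 3 × 60 = 180 patients on LY3074828 and 60 on placebo:

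SE = SD × √(1/180 + 1/60) = SD × 0.149

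- SD 15 ms: SE = 2.2 ms, 95% half-width 1.96 × 15 × 0.149 = 4.4 ms
- SD 20 ms: SE = 3.0 ms, 95% half-width 1.96 × 20 × 0.149 = 5.8 ms

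For one arm against placebo (60 against 60), the half-width 1.96 × SD × √(2/60) is 5.4 to 7.2 ms. On these assumptions the trial is large enough for a by-arm display of mean change to be informative.

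**The case against.** The strongest reply is that little is lost and that the sponsor may drop a secondary analysis. Much of this stands.

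- **Clinically significant findings are still compared.** Protocol 10.3.2.4 and SAP 6.14.6 send them to adverse events, SAP 6.14.2 tabulates treatment-emergent events by treatment, and SAP 6.14 allows all LY3074828 to be compared with placebo. A reader might infer that ECGs yield no group comparison at all. That holds for the measurements, not for findings reported as events.
- **Heart rate is still analysed.** A reader might infer that a heart-rate shift would be missed. SAP 6.14.5 displays pulse by visit and treatment, gives a p-value for change to last observation, and sets high and low criteria in Table 5. In induction, vital signs are taken at Visits 1, 2, 3, 4, 6 and 7, more often than ECGs.
- **A listing may survive.** SAP 6.1 plans a by-patient listing for every SDTM dataset. If ECG results form such a dataset they would be listed, so only the summaries are missing.
- **Interval capture is not established.** The protocol names no set of intervals and describes reading by a site physician, not central measurement. QTcF in the SAP abbreviation list does not show that values were recorded. SAP 6.14.6 says that detailed results are held, yet plans only an occurrence listing.
- **The protocol promised description, not a test,** and the secondary objective is safety and tolerability in general, with no separate ECG objective.

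A reader might also set the remark in the SAP revision history, that no ECG details are collected, against the current 6.14.6. A change log describes superseded text, so it is not evidence of an error and is not used here.

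None of this answers the core point. The freedom to change a non-principal analysis comes with a duty to describe and justify it, and SAP 6.18 says that there is nothing further to describe.

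**Conclusion.** The point holds in a limited form. The protocol and the SAP disagree on whether ECG measurements are summarised by arm, and SAP 6.18 wrongly says that no such disagreement exists. What is lost is the descriptive summary of ECG values and of their change from baseline. The consequence is that average interval shifts below the level of clinical significance would not be seen by arm.

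The conflict rests on the current text alone and needs no assumption. The count of up to 720 tracings assumes full attendance. The standard error of 2.2 to 3.0 ms is illustrative: it rests on an assumed SD, on complete data, and on QTc values actually being in the database, which the sponsor must confirm. The primary endpoint and the efficacy conclusions are unaffected. The change should be made, but it does not threaten the trial's main result.

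**What to change.** First confirm which ECG measurements the database holds.

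**If interval values are held,** as the first sentence of SAP 6.14.6 suggests:
- Replace the closing sentence of 6.14.6 with the protocol's descriptive summary of the measurements captured.
- In induction, show values and change from the Visit 2 baseline to Visit 7, by arm and for LY Total beside placebo.
- In maintenance, show values and change by arm at the scheduled ECG visits, from the protocol's maintenance baseline (the last induction value). State this baseline in 6.14.6, because SAP 6.14 otherwise applies the Week 0 baseline to all quantitative safety analyses.
- Add ECG to the list of safety measures in SAP 6.14. No formal test is needed.

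**If they are not held:**
- Correct the first sentence of 6.14.6.
- List the dropped analysis with its reason in 6.18.
- State that ECG conclusions are limited to adverse events.

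The cost is SAP wording and, in the first case, a few tables from ECGs already scheduled. Neither route needs a new visit or procedure.

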6.14.7. Biomarkers

Samples for the following biomarkers are collected at various timepoints during the trial:

- CRP

- Faecal Calprotectin
- Serum MMP9
- Serum NGAL

Summary tables will be provided by treatment arms at each timepoint the sample was collected.

A graphical representation for the observed value and the change from baseline over time will be presented by treatment group.

The above summaries may be presented separately for each study period if appropriate.

Correlational analysis to determine the relationship of LY3074828 dose levels to biomarker readings will be performed.

Additional correlational analyses to investigate the biomarker readings as a predictor of efficacy outcomes (Clinical remission/response and endoscopic remission) and health outcomes questionnaire findings may be performed if considered useful in further understanding of the study exploratory objectives.

6.14.8. Immunogenicity

Figure 1 provides an overview of the immunogenicity assay process.

At a high level, an individual sample is potentially examined multiple times, in a hierarchical procedure, to produce a sample Anti-Drug Antibodies (ADA) assay result and potentially a sample neutralizing antibody (NAb) assay result. The cut points used, the drug tolerance of an assay, and the possible values of titers are operating characteristics of the assay.

It can be the case that the presence of high concentrations of LY will affect the measurements of the presence of ADA or NAb, and conversely high levels of ADA or NAb may affect the measurement of LY concentration. Thus an LY drug concentration, assessed from a sample drawn at the same time as the ADA sample, plays a key role in clinical interpretation of a sample when the laboratory result is Not Detected, as shown in Figure 1.

The rest of this section defines the component concepts of Figure 1 in greater detail.

6.14.8.1. Definitions of Sample ADA Status

Table 6 Sample ADA Assay Results

[figure not shown]
Sample Laboratory Result	Explanation
Detected	ADA are detected and confirmed.
Not Detected	The raw result as reported from the laboratory indicates not detected. The clinical interpretation of such results depends on other factors (see below).
NO TEST, QNS, etc.	Sample exists but was unevaluable by the assay

Table 7 Sample Clinical ADA Interpretation Results

Sample Clinical Interpretation	Explanation
ADA Present	ADA assay result is Detected
ADA Not Present	
ADA assay result is Not Detected and simultaneous drug concentration is at a level that has been demonstrated to not interfere in the ADA detection method (i.e. drug concentration is below the assay's drug tolerance level).
 
For patients receiving placebo, drug concentration is not assessed and is assumed to be below the assay's drug tolerance level.
 
If drug concentration was planned but is not available for a treatment-period sample, a Not Detected sample will be declared ADA Not Present, on the basis of prior knowledge that the drug tolerance level of the ADA assay is high relative to peak PK levels.

ADA Inconclusive	ADA assay result is Not Detected but drug concentration in the sample is at a level that can cause interference in the ADA detection method.
ADA Missing	ADA sample not drawn, QNS, not tested, etc., causing there to be no laboratory result reported or the result is reported as "no test".

Parallel terminology applies for Neutralizing ADA (NAb) Detected, NAb Not Detected, NAb Present, NAb Not Present, NAb Inconclusive, NAb Missing. ADA and Neutralizing ADA (NAb) are distinct assays and have different assay operating characteristics.

Figure 4 Flow Chart of ADA Sample Assessment with Clinical Interpretation

